#### 13.2.1. Causality Assessment

**Causality Assessment** – A determination of the relationship between an adverse event and the test article. The test article relationship for each adverse event should be determined by the investigator using these explanations:

- Not Related- An adverse event that is not related to the use of the test article, study treatment or study procedures
- Unlikely Related – An adverse event for which an alternative explanation is more likely, e.g. concomitant treatment, concomitant disease(s), or the relationship of time suggests that a causal relationship is not likely
- Possibly Related – An adverse event that might be due to the use of the test article, or to the study treatment or study procedures. An alternative explanation, e.g. concomitant treatment, concomitant disease(s), is inconclusive. The relationship in time is reasonable. Therefore, the causal relationship cannot be excluded
- Related – An adverse event that is listed as a possible adverse effect (device) or adverse reaction (drug) and cannot be reasonably explained by an alternative explanation, e.g. concomitant treatment of concomitant disease(s). The relationship in time is very suggestive, e.g. it is confirmed by de-challenge and re-challenge

#### 13.2.2. Severity Assessment

**Severity Assessment** – A qualitative assessment of the degree of intensity of an adverse event as determined by the Investigator or reported to him/her by the subject. The assessment of severity is made irrespective of test article, study treatment or study procedure relationship or seriousness of the event and should be evaluated according to the following scale:

- Mild – Event is noticeable to the subject, but is easily tolerated and does not interfere with the subject's daily activities
- Moderate – Event is bothersome, possible requiring additional therapy, and may interfere with the subject's daily activities
- Severe – Event is intolerable, necessitates additional therapy or alteration of therapy and interferes with the subject's daily activities

# **Clinical Study Protocol**

## **Johnson & Johnson Vision Care, Inc.**

### **13.3. Documentation and Follow-Up of Adverse Events**

The recording and documenting of adverse events (ocular and non-ocular) begins when the subjects are exposed to the test article, study treatment or study procedure. Adverse events reported before the use of test article, start of study treatment, or study procedures will be recorded as medical history. However, if the condition deteriorates at any time during the study it will be recorded and reported as an AE. Untoward medical events reported after the subject's exit from the study will be recorded as adverse events at the discretion of the Investigator.

Upon finding an adverse event, the Principal Investigator will document the condition in the subject record and in the eCRFs. He/she will complete the Adverse Event /eCRF.

Complete descriptions of all adverse events must be available in the subject record. All Adverse Events including local and systemic reactions not meeting the criteria for "serious adverse events" shall be captured on the appropriate case report form or electronic data system. All adverse events occurring while the subject is enrolled in the study must be documented appropriately regardless of relationship.

It is the Investigator's responsibility to maintain documentation of each reported adverse event. All adverse events will be followed in accordance with applicable licensing requirements. Such documentation will include the following:

- Adverse event (diagnosis not symptom)
- Drawings or photographs (where appropriate) that detail the finding (e.g., size, location, and depth, etc.)
- Date the clinical site was notified
- Date and time of onset
- Date and time of resolution
- Adverse event classification, severity, and relationship to test articles, as applicable
- Treatment regimen instituted, including concomitant medications prescribed, in accordance with applicable licensing requirements
- Any referral to another health care provider if needed
- Outcome, ocular damage (if any)
- Likely etiology
- Best corrected visual acuity at the discovery of the event and upon conclusion of the event

In addition, if an infiltrate(s) is present, he/she will complete the Corneal Infiltrate Assessment eCRF. Where necessary, a culture of the corneal lesion will be collected to determine if the infection is microbial in nature. If cultures are collected, the date of culture collection and laboratory utilized will be recorded.

Changes in the severity of an AE shall be documented to allow an assessment of the duration of the event at each level of intensity to be performed. Adverse events characterized as intermittent require documentation of the onset and duration of each episode. Changes in the assessment of relationship to the Test Article shall also be clearly documented.

# **Clinical Study Protocol**

## **Johnson & Johnson Vision Care, Inc.**

Subjects who present with an adverse event shall be followed by the Investigator, within licensure, until all signs and symptoms have returned to pre-treatment status, stabilized, or been satisfactorily resolved. If further treatment beyond licensure is required, the patient will be referred to the appropriate health care provider. The Investigator will use his/her clinical judgment as to whether a subject reporting with an adverse event will continue in the study. If a subject is discontinued from the study, it will be the responsibility of the Investigator to record the reason for discontinuation. The Investigator will also document the adverse event appropriately and complete the Adverse Event eCRF. Any subjects with ongoing adverse events related to the test article, study treatment or study procedures, as of the final study visit date, should be followed to resolution of the adverse event or until referral to an appropriate health care provider, as recommended by the Investigator. Non-ocular adverse events that are not related to the test article, study treatment, or study procedures may be recorded as "ongoing" without further follow-up.

### **13.4. Reporting Adverse Events**

The Investigator will notify the Sponsor of an adverse event by e-mail, facsimile, or telephone as soon as possible and no later than 24 hours from discovery for any serious /significant adverse events, and 2 days from discovery for any non-significant adverse event. In addition, a written report will be submitted by the Principal Investigator to the IEC/IRB according to their requirements (Section 13.4.2). The report will comment whether the adverse event was considered to be related to the test article, study treatment or study procedures.

#### **13.4.1. Reporting Adverse Events to Sponsor**

##### **Serious/Significant Adverse Events**

The Investigator will inform the sponsor of all serious/significant adverse events occurring during the study period as soon as possible by e-mail, fax, or telephone, but no later than 24 hours following discovery of the event. The Investigator is obligated to pursue and obtain information requested by the Sponsor in addition to that information reported on the eCRF. All subjects experiencing a serious/significant adverse event must be followed up and all outcomes must be reported.

When medically necessary, the Investigator may break the randomization code to determine the identity of the treatment that the subject received. The Sponsor and study monitor should be notified prior to unmasking the test articles.

In the event of a serious/significant adverse event, the Investigator must:

- Notify the Sponsor immediately
- Obtain and maintain in the subject's records all pertinent medical information and medical judgment for colleagues who assisted in the treatment and follow-up of the subject
- Provide the Sponsor with a complete case history which includes a statement as to whether the event was or was not related to the use of the test article
- Notify the IEC/IRB as required by the IEC/IRB reporting procedure according to national regulations

# **Clinical Study Protocol**

## **Johnson & Johnson Vision Care, Inc.**

### **Unanticipated (Serious) Adverse Device Effect (UADE)**

In the event of an Unanticipated (Serious) Adverse Device Effect (UADE), the Investigator will submit a report of the UADE to the Sponsor and IEC/IRB as soon as possible, but no later than 24 hours after the Investigator first learns of the effect. This report is in addition to the immediate notification mentioned above.

The Sponsor must conduct an evaluation of the UADE and must report the results of the evaluation to FDA, the IEC/IRB and participating Investigators within 10 working days after the Sponsor first receives notification of the effect.

### **Non-Serious Adverse Events**

All non-serious adverse events, including non-serious adverse device effects, will be reported to the sponsor by the Investigator no later than 2 days from discovery.

#### **13.4.2. Reporting Adverse Events to the Responsible IEC/IRB and Health Authorities**

Adverse events that meet the IEC/IRB requirements for reporting must be reported within the IEC/IRB's written guidelines. Each clinical site will refer to and follow any guidelines set forth by their Approving IEC/IRB. Each clinical site will refer to and follow any guidelines set forth by their local governing Health Authorities.

The Sponsor will report applicable Adverse Events to the local health authorities according the written guidelines, including reporting timelines.

#### **13.4.3. Event of Special Interest**

None

#### **13.5. Reporting of Pregnancy**

Subjects reporting pregnancy (by self-report) during the study will be discontinued after the event is recorded as an Adverse Event. Once discontinued, pregnant participants and their fetuses will not be monitored for study related purposes. Pregnant participants are not discontinued from contact lens or solution related studies for safety concerns, but due to general concerns relating to pregnancy and contact lens use. Specifically, pregnant women are discontinued due to fluctuations in refractive error and/or visual acuity that occur secondary to systemic hormonal changes, and not due to unforeseen health risks to the mother or fetus.

## **14. STATISTICAL METHODS**

### **14.1. General Considerations**

Statistical Analysis will be undertaken by the sponsor or under the authority of the sponsor. A general description of the statistical methods to be implemented in this clinical trial is outlined below. More details will be included in the stand-alone Statistical Analysis Plan (SAP). The SAP will be developed and finalized prior to database lock.

# **Clinical Study Protocol**

## **Johnson & Johnson Vision Care, Inc.**

All data summaries and statistical analyses will be performed using the SAS software Version 9.4 or higher (SAS Institute, Cary, NC). Throughout the analysis of data, the results for each subject/eye will be used when available for summarization and statistical analysis. Unscheduled visits will be summarized separately and will be excluded from the statistical analysis.

Summary tables (descriptive statistics and/or frequency tables) will be provided for all baseline variables, efficacy variables and safety variables as appropriate. Continuous variables will be summarized with descriptive statistics (n, mean, standard deviation [SD], median, minimum and maximum). Frequency count and percentage of subjects or eyes within each category will be provided for categorical data.

### **14.2. Sample Size Justification**

The sample size was not determined by any empirical power calculation. The plan is to enroll approximately 210-240 subjects with a completion target of 27 subjects per strata (Symptomatic and Asymptomatic). Assuming a sample of size 27 subjects per strata, the statistical power was calculated using SAS procedure PROC POWER. The goal is to show Symptomatic subjects have, on average, lower Non-invasive tear Breaks up Time (NIBUT) and Tear Meniscus Height (TMH); and greater Lid Margin Staining (LMS), Tear Film Osmolarity (OSM), and White Blood Cell (WBC) count compared to Asymptomatic subjects.

Table 4 contains the information of two previous studies and their corresponding subject disposition. Tables 5 to Table 9 below summarizes the primary endpoints from the studies [REDACTED] and [REDACTED] that are corresponded to the current study and therefore used to compute the power.

Table 4: Historical Studies Included

Study	Study Design	Endpoints Collected	No. of Enrolled	No. of Completed - Asymptomatic	No. of Completed - Symptomatic
[REDACTED]	Cross-sectional study of subjects wearing Dailies AquaComfort Plus	Lid Margin Staining, NIBUT, TMH, Tear film osmolarity,	42	25	16
[REDACTED]	Cross-sectional study of subjects	Lid Margin Staining,	74	27	15

# Clinical Study Protocol

## Johnson & Johnson Vision Care, Inc.

	wearing their habitual lenses	White blood Cell Count			
--	-------------------------------	------------------------	--	--	--

Table 5: Lid Margin Staining – Completed Per-Protocol Population [REDACTED]

LMS (Mean [STD]) **	Eyelid	Strata	
		Asymptomatic N=50	Symptomatic N=32
Baseline	Lower	0.98 (0.95)	1.15 (0.75)
	Upper	0.79 (0.75)	0.68 (0.58)
14-Hours Post Lens Insertion	Lower	1.34 (0.77)	1.47 (0.72)
	Upper	0.74 (0.89)	1.31 (0.87)

N=Number of eyes.

Table 6: Non-Invasive Tear Break-Up Time (NITBUT in Seconds) – Completed Per-Protocol Population [REDACTED]

NIBUT (Mean [STD]) **	Strata	
	Asymptomatic N=25	Symptomatic N=16
Post Lens Insertion	13.19 (8.917)	11.47 (7.035)
14-Hours Post Lens Insertion	9.46 (4.608)	8.34 (4.660)

N=Number of Subjects

\*\*Averaged across three measurements

Table 7: Tear Meniscus Height (TMH) – Completed Per-Protocol Population [REDACTED]

TMH (Mean [STD]) **	Eyelid	Strata	
		Asymptomatic N=50	Symptomatic N=16
Baseline	Lower	0.21 (0.054)	0.21 (0.059)
	Upper	0.16 (0.036)	0.017 (0.034)
Post Lens Insertion	Lower	0.20 (0.056)	0.19 (0.048)
	Upper	0.16 (0.041)	0.15 (0.036)
14-Hours Post Lens Insertion	Lower	0.18 (0.065)	0.14 (0.067)
	Upper	0.14 (0.044)	0.12 (0.030)

N=Number of eyes.

\*\*Averaged across three measurements

Table 8: Tear Film Osmolarity (mOsm/L) – Completed Per-Protocol Population [REDACTED]

TOSM (Mean [STD]) **	Strata	
	Asymptomatic N=25	Symptomatic N=16
Post Lens Insertion	319.52 (75.538)	297.47 (10.899)
14-Hours Post Lens Insertion	301.38 (34.473)	288.41 (58.943)

N=Number of Subjects

\*\*Averaged across two measurements

# Clinical Study Protocol

## Johnson & Johnson Vision Care, Inc.

Table 9: Mean White Bloods Cell (WBC) Count (Confocal Microscopy) – Completed Per-Protocol Population [REDACTED]

Mean[STD]	Eyelid	Strata/Eye			
		Asymptomatic N=27		Symptomatic N=15	
		Left	Right	Left	Right
Visit 2 (2-14 Days after Visit 1)	Lower	3.044 (2.7755)	4.062 (4.8873)	6.175 (5.8041)	6.533 (4.1495)
	Upper	3.006 (3.1092)	4.130 (3.9155)	6.277 (6.8528)	5.633 (5.5359)
Visit 3 (2-14 Days after Visit 2)	Lower	2.957 (2.8150)	3.790 (4.7627)	4.444 (4.7879)	6.555 (6.6327)
	Upper	3.197 (3.8542)	4.253 (4.0071)	8.267 (10.5946)	9.301 (10.8690)

N=Number of Subjects [REDACTED]

The power calculation of LMS, NIBUT, TMH, and TOSM were conducted for the combination of the different effect sizes ( $\Delta$  = Symptomatic – Asymptomatic) and the different common variances ( $\sigma$ ). The power calculation of WBC was conducted for the combination of the different mean ratios ( $\phi$  =Symptomatic/Asymptomatic) and the different common coefficient of variances (CV). CV, also known as the relative standard deviation, is the ratio of the standard deviation to the mean.

The parameters  $\Delta$ ,  $\sigma$ ,  $\phi$ , and  $CV$  were estimated from the data of [REDACTED] and [REDACTED]. Historical data suggest that increasing the effect sizes or the mean ratios and decreasing the standard deviation or the coefficient of variations increases the power. For the fixed number of 27 subjects per strata, the criteria that need to be satisfied in order to obtain ~80% power corresponding to the primary hypotheses are presented below in Table 10 to Table 14:

1. Hypothesis 1: Symptomatic subjects will have, on average, greater upper and lower lid margin staining (LMS) compared to asymptomatic subjects after 14 hours of lens wear.

Table 10: Power Calculations of LMS for N=54

Effect size ( $\Delta$ )	Common standard deviation ( $\sigma$ )		
	0.5	0.7	0.9
0.30	70%	46%	33%
0.35	81%	57%	41%
0.40	90%	67%	49%

The sample size is sufficiently large to demonstrate greater LMS with ~80% power to Symptomatic subjects if  $\Delta \geq 0.35$  and  $\sigma \leq 0.5$ .

2. Hypothesis 2: Symptomatic subjects will have, on average, shorter NIBUT compared to asymptomatic subjects after 14 hours of lens wear.

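### Section 14.2: Table 13's osmolarity inputs do not match Table 8, the TMH condition for about 80% power fails inside its own range, and 14.4 (two-sided) contradicts 14.5 (one-sided)

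*Combined protocol and SAP*

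**What the plan says.** Section 14.2 opens by stating "The sample size was not determined by any empirical power calculation". It fixes 27 subjects per stratum and reports power for a grid of inputs. The earlier-study results in Tables 5 to 9 are described as ones "that are corresponded to the current study and therefore used to compute the power", and the effect (symptomatic minus asymptomatic), SD, mean ratio and CV "were estimated from the data of [REDACTED] and [REDACTED". Tables 10 to 14 are introduced as "the criteria that need to be satisfied in order to obtain ~80% power".

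- **Osmolarity.** Table 8 at 14 hours gives mean 301.38 (SD 34.473, n=25) for asymptomatic and 288.41 (SD 58.943, n=16) for symptomatic subjects. Table 4 lists osmolarity for only one of the two earlier studies, so Table 8 is the only osmolarity source shown. Table 13 uses differences of 10, 12 and 14 and SDs of 20, 25 and 30.
- **TMH.** The sentence under Table 12 claims about 80% power when the difference is at or below -0.03 and the SD is under 0.06.
- **Error rate.** Section 14.4 sets a two-sided 5% type I error for every primary and secondary hypothesis. Section 14.5 gives directional hypotheses and one-sided 95% intervals for LMS, NIBUT, TMH, osmolarity and WBC.

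**The concern.** The power tables are the plan's only statement of what 27 per stratum can show. Three things undermine them.

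First, a reader told that the osmolarity inputs were estimated from earlier data will take Table 13 as that study's evidence. The only data shown point the opposite way to Hypothesis 4, and both stratum SDs are above the largest SD in the grid.

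Second, a condition for about 80% power has to hold at its own limits. The TMH condition does not, and Table 12 directly above it shows 57% at (-0.03, 0.06).

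Third, 14.4 and 14.5 give different success rules. A primary result in the hypothesised direction with a one-sided p-value between 0.025 and 0.05 succeeds under 14.5 and fails under 14.4. This affects the primary conclusions as well as the planning figures.

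**Working it through.** **Reproducing the plan's figures.** Take a two-sample t-test with n = 27 per stratum and df = 2n - 2 = 52. The noncentrality is |Δ| / (σ√(2/n)), with √(2/27) = 0.2722. For Table 13 at Δ = 14, σ = 20, the noncentrality is 14 / (20 × 0.2722) = 2.57.

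- One-sided 5% (critical t = 1.675): power 81.4%; the table shows 81%.
- Two-sided 5% (critical t = 2.007): power 71.4%.

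One-sided 5% reproduces every cell of Tables 10 to 14 within 1 point, using a lognormal mean-ratio test with log-scale SD √ln(1+CV²) for WBC. Two-sided 5% does not. The cells are therefore correct for their inputs, and the tables follow 14.5, not 14.4.

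**Osmolarity inputs from Table 8 (14 hours).**

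- Difference: 288.41 - 301.38 = -12.97.
- Pooled SD: √[(24 × 34.473² + 15 × 58.943²)/39] = 45.47. Equal-weight SD: √[(34.473² + 58.943²)/2] = 48.28.
- Pooled SE: 45.47 × √(1/25 + 1/16) = 14.56, 95% CI -42.4 to +16.5. Welch SE: 16.27 on 21.6 df, 95% CI -46.7 to +20.8.

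Power at the most favourable difference in Table 13 (+14), one-sided 5%, 27 per stratum:

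| SD | Origin | Power |
|---|---|---|
| 20 / 25 / 30 | Table 13 | 81% / 65% / 52% |
| 34.5 | Table 8, asymptomatic | 43% |
| 45.5 | Table 8, pooled | 30% |
| 48.3 | Table 8, equal weight | 28% |
| 58.9 | Table 8, symptomatic | 22% |

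The planned model adjusts for baseline. If adjustment scales the SD by √(1 - r²), then bringing 45.47 down to 30 needs r = √[1 - (30/45.47)²] = 0.75, and down to 20 needs r = √[1 - (20/45.47)²] = 0.90. The documents give no correlation.

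**Comparison with the other grids.** The other four grids reach their 14-hour (for WBC, visit) historical spread:

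- LMS: historical SDs 0.72 to 0.89; grid up to 0.9.
- NIBUT: difference 8.34 - 9.46 = -1.12 and SDs 4.608 and 4.660; grid includes -1.1 and SDs up to 5.
- TMH, lower lid: difference 0.14 - 0.18 = -0.04 and SDs 0.065 and 0.067; grid includes -0.04 and SDs up to 0.08.
- WBC: CVs in Table 9 of about 0.64 (4.1495/6.533) to 1.28 (10.5946/8.267); grid 0.65 to 1.3.

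Only the osmolarity grid leaves out its own data.

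**TMH condition, one-sided 5%.**

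| SD | Power at -0.03 | Power at -0.04 |
|---|---|---|
| 0.040 | 85.9% (table 86%) | 97.6% (table 98%) |
| 0.045 | 78.0% | 94.3% |
| 0.050 | 70.2% | 89.5% |
| 0.055 | 63.0% | 83.9% |
| 0.059 | 57.9% | 79.2% |
| 0.060 | 56.7% (table 57%) | 78.0% (table 78%) |

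Solving for 80% gives SD 0.0437 at -0.03 and 0.0583 at -0.04. The stated limit of 0.06 fits the -0.04 row, not the -0.03 row.

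**If 14.4 governs (two-sided 5%).**

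- LMS (0.35, 0.5), NIBUT (-2.1, 3) and osmolarity (14, 20): 81% becomes 71%.
- TMH (-0.04, 0.06): 78% becomes 67%. TMH (-0.03, 0.04): 86% becomes 77%.
- WBC (1.5, 0.65): 80% becomes 69%. WBC (2.0, 1.3): 81% becomes 71%.
- The TMH SD limits for 80% become 0.0386 at -0.03 and 0.0515 at -0.04.

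**The case against.** **Osmolarity.** Power has to be computed in the direction of the alternative, which Hypothesis 4 fixes as positive, and the interval around -12.97 includes +10 to +14. The full reports are not visible, so the inputs may have come from something other than the raw values in Table 8. The planned analysis is baseline-adjusted and allows transformation, and Table 8's four SDs run from 10.9 to 75.5, so they are unstable. The sentence under Table 13 is conditional and correct. All of this stands, and it makes 22-43% an illustration, not a replacement estimate. It does not explain why inputs said to be estimated from these data match them in neither sign nor SD. Nor does baseline adjustment: LMS, NIBUT and TMH are also baseline-adjusted, yet their grids reach the raw SDs.

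**TMH.** The only tabulated SD strictly below 0.06 is 0.04, where power is 86% or 98%, and the failure is confined to differences between -0.03 and about -0.04. That limits the size of the fault. But the sentence is written as a continuous condition and is wrong at its stated effect limit.

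**Sidedness.** Section 14.5 gives an explicit operational rule, so 14.4 could be read as a stray general sentence. That reading is plausible, but 14.4 names the primary hypotheses and nothing in the plan says which section prevails.

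A further point stands: for LMS Model-1 and WBC, 14.5 adjusts across lids and WBC uses a Poisson mixed model, so Tables 10 and 14, and the two-sided figures here, are unadjusted single-comparison approximations.

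**Conclusion.** The concern holds on all three parts.

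- Table 13's inputs disagree with Table 8 in sign (+10 to +14 against -12.97) and in SD (20-30 against about 45 pooled). How they were derived cannot be told from the documents.
- The TMH condition overstates power by up to about 22 points at its own effect limit (58% at SD 0.059 against the claimed 80%).
- Sections 14.4 and 14.5 state incompatible error rates for all five primary tests. The choice moves power by about 10 points at the cells near 80%.

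The figures assume unadjusted two-sample t-tests (lognormal for WBC) with 27 per stratum. Because N was not set by power, the sample size is unaffected, and Table 13's cells are correct for the inputs given. This should be fixed before analysis, chiefly because the primary decision rule must be settled.

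**What to change.** 1. **Osmolarity.** Check Table 8 against the source report and correct it if it is wrong. If it is right, add SDs in the historical range (about 35 to 59) to Table 13, labelled as unadjusted because they may understate the power of the baseline-adjusted model. State that the positive effect is hypothesised and not estimated from those data. If only SDs of 20 to 30 are kept on the ground of baseline adjustment, state the correlation assumed.
2. **TMH.** If testing is one-sided, restate the condition as about 80% power for a difference of -0.03 or beyond with SD up to about 0.044, or -0.04 or beyond with SD up to about 0.058. If two-sided, the SD limits are about 0.039 and 0.051.
3. **Sidedness.** Choose one rule for all five primaries. If one-sided testing is kept, correct 14.4. If two-sided testing is kept, change the hypotheses and intervals in 14.5 and restate Tables 10 to 14 with their accompanying sentences.

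The cost is one check against a source report plus recalculation and rewording in 14.2, 14.4 and 14.5. No subjects, visits or procedures are added. The price is less favourable stated power for osmolarity and TMH, and a loss of about 10 points at the cells near 80% for all five endpoints if testing is two-sided.
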